9.3.1. During Treatment: Clinical Data

During treatment, data should be collected at the end of neoadjuvant chemotherapy, at surgery, at the end of adjuvant chemotherapy, after radiotherapy and at the end of treatment.

The following details should be collected at the end of neoadjuvant chemotherapy:

- Details of chemotherapy given, including drug doses, dates and reason(s) for reductions, delays or discontinuation
 - If neoadjuvant chemotherapy not given, reason should be documented
- Disease status (if assessment carried out)
- Adverse reactions: assessed only in relation to study procedures, e.g. venepuncture, biopsy for research, when applicable

The following details should be collected prior to surgery:

- WHO performance status (patients ≥ 16) or Lansky performance status
- Blood Biochemistry: CRP, albumin, ALP, LDH, creatinine

- Haematology: Hb, ANC, lymphocytes, platelets
- Preoperative imaging
 - Date of MRI
 - Date of CT, if performed
 - Date and type of other imaging, if applicable
 - Disease status

The following surgical details should be collected following surgery for ALL patients on the Surgery eCRF:

- Date and time of surgery
- · Hospital where surgery performed
- Type of surgery (amputation, limb sparing etc.)
- Details of surgical procedure (which anatomical structures removed, use of antibiotics, details on blood loss, whether central line in situ, type of reconstruction, surgical margin assessment etc.)
- ASA classification
- Postoperative complications (wound complications, dehiscence, infection or haematoma requiring return to theatre, thromboembolism, deep implant infection etc.)
- If surgery was planned but not done the reason should be documented.

Pathology

- Maximum dimension on pathology report
- Margins: bone margin, narrowest margin in mm
- Lymphovascular invasion
- Response to chemotherapy, % necrosis
- Was a fresh/frozen specimen stored?
 - If so, where?
 - If not, why not?
- Adverse reactions: assessed only in relation to study procedures, e.g. venepuncture, biopsy for research, when applicable

The following details should be collected at the end of adjuvant chemotherapy:

- Details of chemotherapy given, including drug doses, dates and reason(s) for reductions, delays or discontinuation
- If adjuvant chemotherapy not given, reason
- · Was mifamurtide given? If not, reason why
- Disease status (if imaging assessment carried out)
- Adverse reactions: assessed only in relation to study procedures, e.g. venepuncture

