10. EXPLORATORY BIOLOGICAL STUDIES

The following sections provide an overview of sample collection. For details of sample collection, processing and shipping, refer to the **ICONIC Laboratory Manual**.

Below are two tables outlining biological sample collection for patients receiving either neoadjuvant chemotherapy, or surgery with or without adjuvant chemotherapy. The following sections give further details on processing, collection and storage.

SCHEDULE: PATIENTS RECEIVING SURGERY ALONE +/- ADJUVANT CHEMOTHERAPY	Within 28 days after registration	Surgery	End of Treatment	Follow up	Relapse (local recurrence or metastases)
Whole blood sample for germline DNA	X				
Whole blood sample for ctDNA (optional for all patients)	X		X	Χ¹	Х
FFPE tumour tissue	Х	Х			X ²
Provide information on frozen tumour tissue ³	Х	х	Х		X ²
Frozen tissue samples sent on request	X	Х			X

- 1. To be collected at clinic visit during follow up no more than 6 monthly.
- 2. Collect if patient consents to this optional biopsy (if not already collected as part of SOC)
- 3. Where sample stored, reason sample not taken if applicable

	S.	During Tre	eatment			nce
SCHEDULE: PATIENTS RECEIVING NEOADJUVANT CHEMOTHERAPY	Baseline: within 28 days after registration	End of Neoadjuvant chemotherapy	Surgery	End of Treatment	Follow up	Relapse (local recurrence or metastases)
Whole blood sample for germline DNA	Х					
Whole blood sample for CTCs	х	х	(X) ¹			Х
Whole blood sample for ctDNA (optional for all patients)	х	х	(X) ¹	Х	X ²	Х
PBMCs (UCLH only)	х	Х	(X) ¹	Х		Х
FFPE tumour tissue	х		Х			X ³
Provide information on frozen tumour tissue ⁴	х		х	Х		X ³
Frozen tissue samples sent on request	х		Х			х

- 1. Can collect before primary resection surgery if not taken at end of neoadjuvant treatment
- 2. To be collected at clinic visit during follow up no more than 6 monthly.
- 3. Collect if patient consents to this optional biopsy (if not already collected as part of SOC).
- 4. Where sample stored, reason sample not taken if applicable

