	Assess ctDNA biomarkers for prognostic value by using Cox regression (time-to-event outcomes) and logistic regression (categorical outcomes)
Evaluate whether two methodologies of circulating tumour cell (CTC) detection can isolate and quantify CTCs in patients undergoing neoadjuvant chemotherapy	Identify and quantify CTC numbers at baseline (pretreatment) and changes to CTC numbers in response to chemotherapy Descriptive analysis of CTC numbers as histograms and ranges (min, max, IQR, median)

Power calculations for analysis of biomarkers as predictors of pathological response:

All power calculations assume a fixed 2-sided 5% significance level. As these analyses are hypothesis generating, no adjustments have been made to account for multiple testing.

Stage 1 determined the good pathological response rate to be lower than in clinical trials with 17/43 (37%) having a good response.

Based on data from England (2011-2015), 66% of patients receive surgery and 66% receive chemotherapy. At the outset of Stage 1 we had assumed that 60% of patients receive both treatments. At the end of Stage 1, we determined in our cohort that 72% of patients were planned to receive both modalities of treatment.

We will therefore assume the size of the full dataset of patients treated with both modalities will be at least 65% of 300 patients, thus 195 patients.

1. Serum biomarkers

We expect at least 90% of patients to provide serum samples for biomarker analysis, giving us a cohort size of 176. Assuming an overall pathological response rate of ~40%, and assuming biomarkers will be

categorised based on the median to give an even split (88 per group), below is a summary of the power we will have to detect varying effect sizes:

Alpha	Proportion responding without biomarker (# of responders)	Proportion responding with biomarker (# of responders)	Odds ratio	Risk ratio	Power
0.05	20% (18)	60% (53)	5.9	2.9	99.9%
0.05	25% (22)	55% (48)	3.6	2.2	98.6%
0.05	30% (26)	50% (44)	2.4	1.7	77.8%
0.05	32.5% (29)	47.5% (42)	1.9	1.4	52.9%

2. ctDNA

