At the end of Stage 1, 76 patients had provided baseline samples but on treatment samples were fewer and it was not possible for all patients to have baseline samples collected prior to commencing treatment. We therefore assume that with a total sample size of 300, 150 patients will have sufficient pre-samples to correlate biomarkers with clinical characteristics. Assuming an overall pathological response rate of ~40%, and assuming biomarkers will be categorised based on the median to give an even split (75 per group), below is a summary of the power we will have to detect varying effect sizes:

Alpha	Proportion responding without biomarker (# of responders)	Proportion responding with biomarker (# of responders)	Odds ratio	Risk ratio	Power
0.05	20% (15)	60% (45)	6	3	99.9%
0.05	25% (19)	55% (41)	3.6	2.2	97.0%
0.05	30% (23)	50% (38)	2.3	1.7	70.9%
0.05	32.5% (24)	47.5% (36)	2.0	1.5	46.6%

17.2.2.2: Immune oncology

Biomarkers identified through WGS will be summarised using descriptive statistics (median, range, mean, standard deviation) and assessed as prognostic markers for infiltration (poorly infiltrated vs highly infiltrated) using logistic regression. We assume the overall proportion of patients with high infiltration will be 40% and that biomarkers will be categorised based on the median, to ensure equal numbers of those with and without the biomarker. With 2-sided 5% alpha, our power calculations show that with 150 samples we have >70% power to detect a risk ratio (RR) effect size of RR=1.7 or larger and >95% power to detect an effect size of RR=2.2 or larger. We note that the biomarkers in question here are in fact new therapeutic drug targets, where a strong effect size is required to ensure potential therapeutic efficacy, so biomarkers with more marginal effect (e.g. RR=~1.1-1.5) are not in scope for the study. Hence, we are confident that with 150 patients in our multiplex immunohistochemistry (mIHC) experiment we are well powered to validate novel targets that are significantly different between poorly and highly infiltrated patient groups.

17.2.2.3: Patient Reported Outcomes

We aim to record patient reported outcomes (PROs) over time which are correlated with clinical data for the purposes of identifying factors including prediagnostic pathways which predict lower quality of life, physical function and impaired emotional wellbeing.

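### The serum power table counts everyone who has both surgery and chemotherapy, in any order, but pathological response can be read only after neoadjuvant chemotherapy

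*Protocol*

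**What the plan says.** The relevant part of Protocol 17.2.2.1 is headed "Power calculations for analysis of biomarkers as predictors of pathological response". The test is fixed at the outset: "All power calculations assume a fixed 2-sided 5% significance level".

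The cohort is then built in two steps. First, "We will therefore assume the size of the full dataset of patients treated with both modalities will be at least 65% of 300 patients", which gives 195. This follows a report from Stage 1 that "we determined in our cohort that 72% of patients were planned to receive both modalities of treatment". Second, 90% are expected to provide serum, which gives 176, split at the biomarker median into 88 per group. With an overall response rate of about 40%, the table states power of 99.9%, 98.6%, 77.8% and 52.9% for four pairs of response rates.

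The endpoint is collected under the pathology items of Protocol 9.3.1 as "Response to chemotherapy, % necrosis". Section 10 sets out two sampling schedules, for "patients receiving either neoadjuvant chemotherapy, or surgery with or without adjuvant chemotherapy". Appendix 2 repeats that division, and 9.2.1 allows for primary surgery already performed at baseline.

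**The concern.** The denominator and the endpoint do not match. Necrosis in a resection specimen can reflect only chemotherapy given before the resection. A patient operated on first and given adjuvant chemotherapy has had both modalities and counts towards the 195, but has no chemotherapy response to assess. The protocol makes this distinction elsewhere: Section 10.4 restricts circulating tumour cell sampling to neoadjuvant patients. The response denominator does not make it, and the only deduction from 195 is the 10% without serum.

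At stake is whether the stated power describes an analysis the cohort can deliver. The consequence falls mainly on the two smaller-effect rows, where power is sensitive to the number of patients.

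**Working it through.** **Inputs, all from Protocol 17.2 unless noted.** Total 300; both modalities 65%; serum 90%; median split; two-sided alpha 0.05; response pairs 20% v 60%, 25% v 55%, 30% v 50% and 32.5% v 47.5%. The share of both-modality patients operated on first, s, is not reported; 10% to 30% is assumed here.

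**Step 1: reproduce the stated cohort.** 300 × 0.65 = 195; 195 × 0.90 = 175.5, stated as 176, or 88 per group.

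**Step 2: reproduce the stated power.** For n per group, d = |p1 − p2| and p̄ = (p1 + p2)/2, the pooled normal approximation without continuity correction is

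power = Φ( [d√n − 1.96 √(2p̄(1 − p̄))] / √(p1(1 − p1) + p2(1 − p2)) ).

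For 30% v 50% and n = 88: d√n = 0.2 × 9.381 = 1.876; 1.96 × √0.48 = 1.358; denominator √(0.21 + 0.25) = 0.678. So Φ(0.518/0.678) = Φ(0.764) = 77.8%. The other rows give 99.99%, 98.6% and 52.9%. All four agree with the protocol, so its arithmetic is sound and only the denominator is in question.

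**Step 3: remove surgery-first patients.** Evaluable serum cohort = 195 × (1 − s) × 0.90.

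| Assumed s | Serum cohort | 20% v 60% | 25% v 55% | 30% v 50% | 32.5% v 47.5% |
|---|---|---|---|---|---|
| As stated | 176 | 99.9% | 98.6% | 77.8% | 52.9% |
| 10% | 158 | >99.9% | 97.6% | 73.2% | 48.6% |
| 20% | 140 | 99.9% | 96.0% | 68.0% | 44.1% |
| 30% | 123 | 99.8% | 93.4% | 62.1% | 39.5% |

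Even s = 5% gives about 167 patients and 75.5% for 30% v 50%.

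**Step 4: how much the 65% could absorb.** If all of the 72% planned in Stage 1 were treated with both modalities, 195 would still be reached with s up to 1 − 65/72 = 9.7%.

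**Step 5: a larger total.** Protocol 1.1 gives a target accrual of at least 350. Then 350 × 0.65 × 0.90 = 204.75 before any deduction. With s = 10% it is about 184 (79.6% for 30% v 50%), and with s = 20% about 164 (74.7%).

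**Step 6: what Stage 1 shows.** Response is reported for 43 patients. The ctDNA paragraph says: "At the end of Stage 1, 76 patients had provided baseline samples". Enrolment was therefore at least 76, and 43/76 = 56.6% is the most that had a result at that time, against 65% assumed. Scaled up, 300 × 0.566 × 0.90 = 153 patients and 71.7% for 30% v 50%. This is indicative only, for the reasons given under the objection.

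**The case against.** The best defence is that the plan has slack. It uses 65% after seeing 72% planned, and 300 although 1.1 aims for at least 350. At 350 and 65%, about 14% of the serum cohort could be lost before it fell below 176 (1 − 176/204.75); at 350 and 72%, about 22% (1 − 176/226.8). These margins are real, and they mean an overstatement is not proved at low surgery-first shares. But the protocol does not assign them to treatment order. The gap between 72% and 65% must also cover planned treatment not delivered and missing necrosis results, and 17.2.2.1 itself works from 300.

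It is also fair that these analyses are declared hypothesis generating, that no target power is set, and that 17.1 takes the total of 300 from expected recruitment and not from this table. That limits the importance of the point. The SAP may define the analysis set, but the cohort size and power are stated in the protocol and rest on the wider group.

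Two stronger readings are tempting and do not stand:

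- **Bias.** Because 9.3.1 says "The following surgical details should be collected following surgery for ALL patients on the Surgery eCRF" and the necrosis item follows, a reader might infer that surgery-first patients are scored as poor responders, diluting associations. No section codes an inapplicable necrosis result as non-response. Section 11.3 provides a Not Applicable entry, and Stage 1 reported response over 43 patients only.
- **Stage 1 as proof of size.** A reader might set 43 against 76 × 0.72 = 54.7 and take the shortfall as the surgery-first share. But 76 counts optional ctDNA samples, 72% is planned treatment, and the 43 is a snapshot. The shortfall may reflect surgery still pending, plans not delivered or missing pathology reports.

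**Conclusion.** The point holds as a mismatch between denominator and endpoint. The 176 and its four power figures are correctly computed for patients who receive both treatments. They are not supported for patients in whom response to chemotherapy can be read.

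The size rests on an assumed surgery-first share. Over 10% to 30% of the 195, power for 30% v 50% is about 73% to 62% instead of 77.8%, and for 32.5% v 47.5% about 49% to 40% instead of 52.9%. The two larger-effect rows stay above 93%, so conclusions about strong biomarkers are unaffected. If the whole 72% were treated as planned and the share were below about 10%, the stated cohort could still be reached. The documents do not establish any single replacement figure.

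**What to change.** In Protocol 17.2.2.1, define the pathological-response set as patients resected after neoadjuvant chemotherapy who have a necrosis result. Report the proportion of Stage 1 patients who met that definition, among those with enough follow-up to have reached surgery; the sponsor holds these data. Restate the serum cohort and all four power rows from that proportion, and say what the difference between 72% and 65% is meant to cover.

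The cost is a wording change, one tabulation of existing Stage 1 data and a recalculated table, possibly with lower stated power. No extra patients or data collection are needed.

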2. BACKGROUND AND RATIONALE

Osteosarcoma (OS) is the most common bone sarcoma, accounting for approximately 30% of all bone sarcoma diagnoses. In England, it accounts for approximately 130 cases per year across all ages (Table 1). Age-specific overall survival incidence rates are generally bimodal, with the first peak in adolescence and a second peak in patients over 60 years of age. Treatment is multimodal, including multi-agent chemotherapy and surgery to the primary site and to metastases where appropriate. Outcome, however, has improved little over the past 25 years with 5-year survival rates remaining about 42% for all ages and stages in the UK. Five-year relative survival rates are significantly higher for patients <40 years of age (52%) compared with patients over 40 years (25%)¹. Survival is also dependent on the primary site of disease, and is poor for patients with non-extremity tumours, at 36% for patients under the age of 40 years and as low as 6% for patients over 40 years. Outcome for patients with metastatic disease at diagnosis remains equally poor²-5. The use of chemotherapy and surgery varies according to factors such as age, primary site, stage and performance status with approximately two thirds currently receiving these treatments in England each year (Table 1).

Age (years)	< 40	%	40-59	%	60 +	%	Total No.	%
Total	86	63	20	15	31	22	136	100
Chemotherapy	70	82	13	65	6	19	89	66
Surgery	64	75	13	65	13	42	90	66

Table 1. Average number of patients diagnosed per year with OS receiving chemotherapy and/or surgery in England (2011-2015)^{\$}

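### The ctDNA power table for pathological response takes its 150 patients from all 300, without the both-treatments restriction that the serum table applies, so its stated powers hold only if all 150 have an assessed response

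*Protocol*

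**What the plan says.** All in the protocol, section 17.2.2.1 unless noted.

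- Both tables stand under one heading: "Power calculations for analysis of biomarkers as predictors of pathological response". On the significance level: "All power calculations assume a fixed 2-sided 5% significance level".
- Three figures are given for the share of patients having both treatments. The planning figure: "At the outset of Stage 1 we had assumed that 60% of patients receive both treatments". The Stage 1 finding: "we determined in our cohort that 72% of patients were planned to receive both modalities of treatment". The value adopted: "full dataset of patients treated with both modalities will be at least 65% of 300 patients, thus 195 patients".
- Serum: 90% of patients are expected to give samples, so the cohort is 176, or 88 per group.
- ctDNA: 76 patients had given baseline samples by the end of Stage 1. On-treatment samples were fewer, and not all baseline samples could be taken before treatment began. Then: "We therefore assume that with a total sample size of 300, 150 patients will have sufficient pre-samples to correlate biomarkers with clinical characteristics". With about 40% responding and a median split there are 75 per group. The stated power is 99.9% for 20% v 60%, 97.0% for 25% v 55%, 70.9% for 30% v 50% and 46.6% for 32.5% v 47.5%.
- ctDNA sampling is optional and open to all consenting patients (sections 9.2.4 and 10.5). Response to chemotherapy, as percent necrosis, is recorded with the surgical pathology (section 9.3.1).

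**The concern.** A patient without preoperative chemotherapy and a resected specimen has no pathological response and cannot enter this table. The protocol recognises this when it cuts 300 to 195 and builds the serum cohort on that number. The ctDNA paragraph then goes back to 300 as its base, counts patients with enough samples to relate to clinical characteristics, and in the next sentence treats every one of them as evaluable for response. No step links the two.

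If some of the 150 lack the endpoint, the table overstates the power. Whether ctDNA predicts response is a named Stage 2 question, so a null result could be set against a figure that the evaluable cohort does not deliver.

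**Working it through.** **Inputs.** Two-sided alpha 0.05; response 30% v 50% in the row of most interest; 150 patients with ctDNA samples; both-treatments share 65%, with 60% and 72% also given (all section 17.2.2.1); treatment counts from Table 1 in section 2.

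**Formula.** Two-proportion normal approximation with pooled null variance and no continuity correction, n per group, p̄ = (p1 + p2)/2:

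Power = Φ( [ |p1 − p2| − 1.96·√(2p̄(1 − p̄)/n) ] / √( [p1(1 − p1) + p2(1 − p2)]/n ) )

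**Reproducing the plan.** At n = 75 for 30% v 50%: the numerator is 0.2 − 1.96·√(0.48/75) = 0.2 − 0.1568 = 0.0432; the denominator is √(0.46/75) = 0.0783; Φ(0.55) = 70.9%, as stated. The other ctDNA rows give 99.96%, 97.0% and 46.6%. At n = 88 the formula also returns the serum values of 98.6%, 77.8% and 52.9%. The power arithmetic is therefore right, and the only open point is the number of evaluable patients.

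**The two bases side by side.**
- Serum: 300 × 0.65 = 195; 195 × 0.90 = 175.5, given as 176.
- ctDNA: 150 out of 300, with no 65% step. If the 150 were all inside the 195, the sampling rate there would be 150/195 = 77%.

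**With the protocol's 65% applied.** 150 × 0.65 = 97.5, or 49 per group. For 30% v 50%: (0.2 − 0.1940)/0.0969 = 0.06; Φ(0.06) = 52.5%.

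| Response rates | Stated (75 per group) | 49 per group |
|---|---|---|
| 20% v 60% | 99.9% | 98.9% |
| 25% v 55% | 97.0% | 87.0% |
| 30% v 50% | 70.9% | 52.5% |
| 32.5% v 47.5% | 46.6% | about 33% |

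**Power for 30% v 50% by share of the 150 with the endpoint.**

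| Share | Where it comes from | Patients | Power |
|---|---|---|---|
| 60% | planning figure at the outset of Stage 1 | 90 | 49.0% |
| 65% | value adopted for Stage 2 | 97.5 | 52.3% |
| 72% | planned treatment at the end of Stage 1 | 108 | 56.6% |
| 86% | Table 1, treated patients only: 83/96 | about 130 | 64.5% |
| 97% | 66%, 66% and 65% both: 65/67 | about 146 | 69.6% to 69.8% |
| 100% | all 150 inside the 195 | 150 | 70.9% |

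The 86% row takes the largest overlap that Table 1 allows by age group (64 + 13 + 6 = 83) over treated patients (89 + 90 − 83 = 96). The 97% row takes 65 over 66 + 66 − 65 = 67. Both assume that only treated patients are sampled and that sampling is unrelated to modality among them.

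**The case against.** A reader might infer that the true power for 30% v 50% is about 52%. The documents do not support that as a fact. It assumes that ctDNA sampling is unrelated to treatment, and nothing in the protocol says so. The study summary in section 1.1 ties blood collection to patients receiving chemotherapy and/or surgery, and the sample schedules in sections 1.2 and 10 cover only a surgery group (with or without adjuvant chemotherapy) and a neoadjuvant group. Among treated patients the share with both modalities could be 86% or more, which puts power at about 65% to 70%. The 150 also fits arithmetically inside the 195, in which case 70.9% stands. This argument holds, and it is why the result is given as a range.

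It does not clear the table. The surgery schedule includes a baseline ctDNA sample, yet surgery followed by adjuvant chemotherapy yields no preoperative response, so the 86% and 97% shares are themselves generous. The paragraph names 300 as its base and offers nothing for 77% sampling. Stage 1 had 76 patients with baseline samples but reports response for 43, at most 57% of the 76. Some results may have been pending, so this is indicative only.

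A reader might also extend the criticism to the serum table, because Table 1 allows at most 83/136 = 61% with both treatments. That does not carry weight: 65% is a disclosed planning choice below the cohort's own 72%, and a 61% share moves the 77.8% only to about 75%.

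Finally, the analyses are labelled hypothesis generating, the table sets no sample size, and 300 is a minimum. With 350 patients and the same fractions (350 × 0.5 × 0.65, about 114), power is about 59%. These points limit the severity but do not repair the base.

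**Conclusion.** The point holds as a flaw in the base of the ctDNA table, not in its arithmetic. The stated 97.0%, 70.9% and 46.6% require all 150 patients to have neoadjuvant chemotherapy and an assessed resection. The protocol does not state this, and its description of pre-treatment sampling gives no support for it. On the protocol's own 65% the powers are about 87%, 52% and 33%. For 30% v 50% the plausible span runs from 49% to 57% at shares of 60% to 72%, up to about 65% to 70% if nearly all sampled patients receive both treatments. Which value applies depends on an overlap that the document does not give. Because the analysis is hypothesis generating and no sample size rests on it, this is a should-fix.

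**What to change.** State how many patients are expected to have both a pre-treatment ctDNA sample and an assessed pathological response, taking the overlap from the Stage 1 data, and recompute the four ctDNA powers on that number. If 150 of the 195 was intended, say so and justify 77% pre-treatment sampling in that group. The serum table can stay. So can the 150 in the immune-oncology section, since infiltration does not depend on a response assessment.

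The cost is a sentence and one table in the protocol, with stated powers that will probably be less favourable. No additional patients or samples are needed.
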